14.0 Resources and Qualifications

14.1 Describe the qualifications (e.g., education, training, experience, expertise, or certifications) of the Principal Investigator **and** staff to perform the research. When applicable describe their knowledge of the local study sites, culture, and society. Provide enough information to convince the IRB that you have qualified staff for the proposed research.

NOTE: If you specify a person by name, a change to that person will require prior approval by the IRB. If you specify a person by role (e.g., coordinator, research assistant, co-investigator, or pharmacist), a change to that person will not usually

require prior approval by the IRB, provided that the person meets the qualifications described to fulfill their roles.

Response: All study personnel are educated, trained, and licensed as required for their delegated role in this study. All study personnel have also received the required university training and will be trained by the PI before the study starts.

Describe other resources available to conduct the research.

14.2 Describe the time and effort that the Principal Investigator and research staff will devote to conducting and completing the research.

NOTE: Examples include the percentage of Full Time Equivalents (FTE), hours per week. The question will elicit whether there are appropriate resources to conduct the research.

Response: The principal investigator supervises the research project and weekly research meetings are conducted to discuss the recruitment rate, resolve and discuss issues related to the conduct, safety, analysis of the study and related publications. PI is expected to spend 5% of his academic time on this research. The co-investigators and study coordinator provide coverage to the research related activity for 365 days a year.

14.3 Describe the availability of medical or psychological resources that subjects might need as a result of anticipated consequences of the human research, if applicable.

NOTE: One example includes: on-call availability of a counselor or psychologist for a study that screens subjects for depression.

Response: Available medical literature will be provided as deemed appropriate or requested by patient through UB libraries, Pubmed, Google scholar as all the investigators have access to medical literature through listed resources above

The patient will also have access to physician (Investigators and Co-Investigators) who will be available to address any adverse effects or other questions during the course of the study who will be available to address any adverse effects or other questions during the course of the study

14.4 Describe your process to ensure that all persons assisting with the research are adequately informed about the protocol, the research procedures, and their duties and functions.

Response: Education through training, meetings, conferences and discussions.

15.0 Other Approvals

15.1 Describe any approvals that will be obtained prior to commencing the research (e.g., school, external site, funding agency, laboratory, radiation safety, or biosafety).

Response:

N/A: This study does not require any other approvals.

16.0 Provisions to Protect the Privacy Interests of Subjects

16.1 Describe how you will protect subjects' privacy interests during the course of this research.

NOTE: Privacy refers to an individual's right to control access to him or herself. Privacy applies to the person. Confidentiality refers to how data collected about individuals for the research will be protected by the researcher from release. Confidentiality applies to the data.

Examples of appropriate responses include: "participant only meets with a study coordinator in a classroom setting where no one can overhear", or "the participant is reminded that they are free to refuse to answer any questions that they do not feel comfortable answering."

Response: Our clinical providers involved in the study will identify potential patients for recruitment from the Diabetes-Endocrinology Center of WNY Clinics according to the inclusions and exclusion criteria and through advertisements. Patient who qualify will be asked in private during their one on one consultation time with the physician if they wish to participate in the research study. If the patient agrees, the research coordinator will contact them for a telephone screening privately. The patients who call for potential participation in the study due to advertisement flyers will be screened over the phone with the research coordinator, using our telephone screening form.

When the patient is being seen at our clinics for the first time they sign the "Consent to use and disclosure of protected health information" form which clearly states that their protected health information (PHI) can be used for review in preparation for possible research.

If the patient passes the telephone screening, they will be asked to make an appointment to review and sign the consent. Patient will do this in a private, screen off area of the research department and will be allowed to discuss the consent in detail with the research coordinator and or study doctor. Patient will be no notified that it is completely voluntary to participate in the research study and can withdraw at any time.

We will not be accessing any medical information of the patients for whom the services are not provided by our clinic providers.

16.2 Indicate how the research team is permitted to access any sources of information about the subjects.

NOTE: Examples of appropriate responses include: school permission for review of records, consent of the subject, HIPAA waiver. This question **does apply** to records reviews.

Response: Consent of the subject and partial HIPAA waiver.

17.0 Data Management and Analysis

17.1 Describe the data analysis plan, including any statistical procedures. This section applies to both quantitative and qualitative analysis.

Response: The focus of the proposed research is to evaluate the effect of liraglutide on mean HbA1c% over the period of 26 weeks of treatment. The similarities between the study groups, baseline values for subject's demographics and study endpoints will be compared using appropriate parametric tests. Transformations of the data in order to meet statistical assumptions may be considered. The **primary endpoint** of the study is to detect

a difference in HbA1c after 26 weeks of treatment with Liraglutide or placebo. The statistical analysis will be carried out using analysis of covariance (ANCOVA) and tested at the 0.05 level. Change in weight will be a covariate. The results will be computed as mean \pm SD. Analysis will be carried out on the basis of intention to treat (with last observation carried forward).

The secondary end points based on glycemic changes will include the difference from baseline in mean weekly glucose concentrations, standard deviations of the mean weekly glucose concentrations, HbA1c, fructosamine, the duration of time spent in hyperglycemia ($>150\text{mg/dl}$, $>200\text{mg/dl}$, $>250\text{mg/dl}$) and hypoglycemia ($<70\text{mg/dl}$, $<40\text{mg/dl}$), insulin dosage. A reduction in the AUC following the meal will constitute another secondary end point. Between groups comparisons of the magnitude of change from baseline will also be made for these glycemia related secondary endpoints using student's t-test. Comparisons for these and the primary endpoints will also be made using the paired t-test or Wilcoxon's test for paired data within each group.

The other secondary end-points of the study will be change from baseline after 26 weeks of treatment in the fasting and postprandial blood sugars, glucagon and C-peptide concentrations, indices of oxidative and inflammatory stress in MNC, plasma and adipose tissue; subcutaneous fat mass, hepatic fat content and visceral fat mass; features of metabolic syndrome; gastric emptying, blood pressure, vascular analysis, patient reported nausea, quality of life and depression scores. Between groups comparisons will be made using students t-test or ANCOVA (adjustment will be done for baseline differences). Within group comparisons for these endpoints will be made using paired t-test or Wilcoxon's test or ANCOVA.

17.2 If applicable, provide a power analysis.

NOTE: This may not apply to certain types of studies, including chart/records reviews, survey studies, or observational studies. This question is asked to elicit whether the investigator has an adequate sample size to achieve the study objectives and justify a conclusion.

Response: There are no prior randomized controlled trials that have examined the effect of Liraglutide on HbA1c in subjects with type 1 diabetes. In our observational study (preliminary data), we found a decrease in HbA1c of 0.35% after 6 months of liraglutide in patients with type 1 diabetes who had a mean HbA1c of $6.45\pm0.5\%$. In our proposed study, we will include patients with HbA1c up to 8.5%. Thus we expect a greater difference in HbA1c among the two groups at the end of the study. Conservatively estimating a difference in HbA1c of 0.35% between the two groups, a sample size of 32 patients per treatment group should provide 80% power to detect a significant difference ($\alpha = 0.05$), provided the standard deviation of the residuals is not greater than 0.5. Thus 64 subjects will be needed for the study. To account for a dropout rate of 30%, we will recruit 84 subjects into the study.

17.3 Describe any procedures that will be used for quality control of collected data.

Response: Three investigators and research nurse will double check the accuracy of collected data. All laboratory testing will be standardized using references and standards.

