2.0 Scientific Endpoints

2.1 Describe the scientific endpoint(s), the main result or occurrence under study.

NOTE: Scientific endpoints are outcomes defined before the study begins to determine whether the objectives of the study have been met and to draw conclusions from the data. Include primary and secondary endpoints. Some example endpoints are: reduction of symptoms, improvement in quality of life, or survival. Your response should **not** be a date.

Response: **Primary endpoint:** Change from baseline in HbA1c at 26 weeks as compared to placebo. **Secondary endpoints:** Change from baseline as compared to placebo in a)fasting and postprandial blood sugars, mean weekly glucose concentrations, standard deviation of weekly blood sugars and fructosamine; b)fasting and postprandial glucagon and C-peptide concentrations; c)insulin doses; d)indices of oxidative and inflammatory stress in MNC, plasma and adipose tissue; e)oxidative and inflammatory stress in plasma

and MNC following meal challenge; f)subcutaneous fat mass, hepatic fat content and visceral fat mass; g)waist circumference, blood pressure, triglycerides, HDL cholesterol and incidence of metabolic syndrome; h)gastric emptying; i) 24 hour blood pressure; j) flow mediated dilatation in brachial artery, k) SF-36 score; l) depression (PHQ) score.

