1. This will be the first prospectively randomized controlled study to investigate the effect of liraglutide on glycemic levels and variability in overweight and obese type 1 diabetes treated with insulin alone. Liraglutide is the preferred agent for this study since its pharmacokinetics and pharmacodynamics ensure a duration of action of 24 hours. Hitherto, the treatment of type 1 diabetes is based on insulin replacement with novel analogs with appropriate pharmacodynamic profiles or with unique insulin delivery systems. The concomitant use of metformin or pramlintide helps in some patients but the benefits are far from consistent and, therefore, these agents have not made an impact on the treatment of this condition(6).
2. This will be the first study to investigate the role of glucagon and the potential basal and postprandial suppression of glucagon by liraglutide in the pathogenesis and control of glycemia in type 1 diabetics. This is particularly important since in the absence of insulin secretion from the β -cell, there is no paracrine inhibition of glucagon secretion by the α -cell. GLP-1 analogs are known to suppress glucagon(5).
3. With the use of CGM, this study will determine the rapidity of response by liraglutide, which in our preliminary study was observed within the first two days such that we advised patients to reduce their insulin doses by 25% in advance.
4. This will be the first study to attempt to reduce body weight and other features of the metabolic syndrome, while improving glycemic control with addition of a single therapeutic agent in overweight and obese patients with type 1 diabetes. This is particularly relevant since insulin induces weight gain and 40-50% of type 1 diabetics in the US have the metabolic syndrome(14). Liraglutide and the only other licensed drug in this class, exenatide, have been shown not only to reduce body weight but also

to reduce systolic blood pressure plasma triglyceride and CRP concentrations in subjects with type 2 diabetes(8; 9; 15; 16; 18).

- Finally, it will allow us to assess whether liraglutide can activate the dormant β -cells which are known to survive in type 1 diabetics for a long time (19). An analysis in a subset of the study patients with detectable C-peptide will be carried out separately. This will assess the effect of liraglutide in preserving β -cells and the effect of residual β -cell function on the action of liraglutide

Liraglutide treatment in patients with type 1 diabetes

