As mentioned above, the treatment of 14 type 1 diabetes patients; age (38.5 years), duration of diabetes (20 ± 4 yrs), weight (66 ± 6 kg), HbA1c% (6.5 ± 0.5 %), C-peptide (< 0.10 nmol/l), basal insulin dose of 24 ± 6 units/day, bolus insulin dose of 22 ± 4 units/day with liraglutide in addition to insulin resulted in significant reduction in fasting and mean blood glucose concentrations, insulin doses by 45%, HbA1c levels even at 24 weeks, and a reduction in appetite and caloric intake with weight loss. In addition, there was a reduction in the excursions of blood glucose concentrations, i.e., the standard deviations of blood glucose concentrations were markedly reduced. The changes were observed within 48h and improved marginally thereafter with fine tuning of insulin doses and a further reduction in these doses. The comparison of changes observed early (1 week) vs late (9 weeks) are evident in **tables 1 and 2**. These observations are noteworthy in that they were made in patients who had been well controlled, were meticulous, even obsessive, and were on CSII and CGM. They had all tried hard to improve their diabetic control by adjusting insulin doses but had not succeeded because of the induction of hypoglycemia. To establish this fact, the patients recorded their glucose concentrations for at least two weeks during which optimal control was attempted and no significant change was observed (data not shown). While our initial plan was to assess the effect with one week treatment, 7 patients wanted to continue with Liraglutide and were able to get insurance coverage for this treatment. This study was conducted to improve glycemic control in the clinic and not as a randomized or placebo controlled trial. In view of the significant effects that were observed (**Figure 1**), we now want to conduct a prospective randomized placebo controlled trial to investigate and confirm these effects of Liraglutide in subjects with type 1 diabetes.

Table 1) Effects of Liraglutide after treatment for one week (n=14)

[figure not shown]
Table 1	Before treatment	On Liraglutide	P value
Weight(kg)	66 ± 6	65 ± 5	0.22
insulin dose (basal)	24 ± 6 U/d	16 ± 6 U/d	<0.01
insulin dose (bolus)	22 ± 4 U/d	15 ± 4 U/d	<0.01
Mean Fasting Blood Glucose (mg/dl)	129 ± 10	110 ± 8	0.02
Weekly Mean Blood Glucose (mg/dl)	141 ± 20	115 ± 12	<0.01
Time spent in hypoglycemia <70 mg/dl(% time)	2.1 ± 2	2.6 ± 2	0.08
Time spent in hypoglycemia <40 mg/dl(% time)	0.12 ± 0.2	0.16 ± 0.3	0.09

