Study Visit day 0: Subjects will come fasting for this visit. Each subject will be given one injection of Liraglutide 1.2 mg or placebo. A fructosamine and blood samples will be collected at baseline. Blood samples will be collected after the baseline at 30, 60, 120, 180, 240 and 300 minutes after the injection. (**This is being done to evaluate the acute effect of a single injection of Liraglutide on oxidative stress and inflammatory mediators, before any adjustments of insulin dose or effect of Liraglutide on blood glucose and weight is evident**). Subjects will be instructed by the study staff in the dosing and administration of the study medication. They will start Liraglutide injection at a dose of 0.6 mg per day or placebo injection on the following day. We will adjust the doses of basal and bolus insulin to eliminate low blood sugars(less than 70 mg/dl). At all subsequent visits insulin doses will be titrated to target blood sugars between 70-180 mg/dl at all times. Patients will return to the center after 7 days.

Study Visit week 1: Blood glucose concentrations will be reviewed. Insulin dose will be adjusted at the discretion of the study investigator to optimize blood sugar control as per

the targets mentioned above. Patients will be advised to increase the Liraglutide dose to 1.2 mg a day if they are able to tolerate the 0.6 mg dose. If they are experiencing mild nausea, subjects will continue with 0.6 mg daily for another 7 days. Those with severe nausea/vomiting will be dropped from the study. All other subjects will return in 7 days.

Study Visit week 2: Blood glucose concentrations will be reviewed. Insulin dose will be adjusted if needed. Subjects taking 0.6 mg dose and experiencing significant nausea will be dropped from the study. Subjects on 1.2 mg and experiencing significant nausea will decrease the dose to 0.6 mg and continue that dose for the duration of the study. Subjects on 1.2mg and experiencing mild nausea will continue on 1.2 mg for 2 more weeks. Subjects on Liraglutide 1.2mg daily without any gastro-intestinal side-effects will be asked to increase the dose to 1.8 mg daily. Study drug will be dispensed for additional 2 weeks.

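### The primary HbA1c ANCOVA adjusts for change in weight, a post-randomisation effect of liraglutide, so the 0.05 test does not in general address the stated endpoint

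*Combined protocol and SAP*

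**What the plan says.** Section 2.1 defines the primary endpoint as "Change from baseline in HbA1c at 26 weeks as compared to placebo". Section 17.1 tests it by ANCOVA at the 0.05 level, then adds "Change in weight will be a covariate". No baseline covariate is named for this model. Adjustment for baseline differences appears only later, for the non-glycaemic group of secondary endpoints.

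The same section lists HbA1c again among the glycaemic secondary endpoints, for which it says "Between groups comparisons of the magnitude of change from baseline will also be made for these glycemia related secondary endpoints using student's t-test". An unadjusted HbA1c comparison is therefore planned, but as a secondary analysis.

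Section 3.1 treats weight as something the drug changes. Item 4 of the innovation list says "This will be the first study to attempt to reduce body weight and other features of the metabolic syndrome, while improving glycemic control". The preliminary data report "a reduction in appetite and caloric intake with weight loss", and Table 2 shows mean weight going from 68 to 64 kg (n=8, P=0.02).

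Section 17.2 powers the trial for an HbA1c difference of 0.35 between groups with 32 per arm, "provided the standard deviation of the residuals is not greater than 0.5". It does not say which model those residuals come from.

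**The concern.** Randomisation protects the comparison of arms as assigned. It does not protect a comparison made at equal values of something the treatment has altered. Two mechanisms matter here.

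- **Mediation.** Weight loss may carry part of the HbA1c effect. Holding weight change fixed removes that part.
- **Shared post-randomisation causes.** Insulin dose can affect both variables. Section 10.1 (day 0) says "At all subsequent visits insulin doses will be titrated to target blood sugars between 70-180 mg/dl at all times", and Section 3.1 says "insulin induces weight gain". Conditioning on weight change can then create an association between arm and HbA1c, of either sign, that is not an effect of assignment.

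At stake is the trial's only primary test. The weight-adjusted coefficient could hide a real benefit, overstate it, or be significant when the arms do not differ overall in HbA1c.

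**Working it through.** **The plan's own figure.** Normal approximation, two-sided 0.05, 80% power: n per arm = 2 × [0.5 × (1.960 + 0.842) / 0.35]² = 32.04. The stated 32 per arm reproduces (power 79.96%; 78.7% with the t distribution). This calculation is for the total difference of 0.35, with no weight term.

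**Inputs for the model as written**
- From Section 17.2: 32 per arm, difference 0.35, residual SD 0.5.
- SD of weight change, s: not in the documents. Back-calculated from Table 2, assuming its P value is from a paired t-test: s = 4 × √8 / 2.998 = 3.77 kg (3.53 to 3.98 if the rounded P of 0.02 lies between 0.015 and 0.025).
- Arm difference in weight change, D: assumed 2 to 4 kg. The upper end is the uncontrolled pilot change.
- Within-arm slope b, HbA1c points lost per kg lost: not in the documents. Assumed 0, 0.02, 0.05 and, in the opposite direction, −0.02.

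**Formulas**
- Variance inflation from the correlation of weight change with arm: VIF = 1 + (D/s)²/4.
- Expected adjusted estimate: 0.35 − b × D.
- Standard error: 0.5 × √(2/32) × √VIF = 0.125 × √VIF. Power is from the noncentral t on 61 df (62 without the covariate).

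VIF is 1.070 at 2 kg, 1.158 at 3 kg and 1.281 at 4 kg. The correlations of weight change with arm are 0.26, 0.37 and 0.47, which is modest to moderate.

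**Results when the true difference is 0.35** (78.7% power without the covariate)

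| Slope b | Estimate, D = 2 | Power, D = 2 | Estimate, D = 4 | Power, D = 4 |
|---|---|---|---|---|
| 0 | 0.35 | 75.9% | 0.35 | 68.3% |
| 0.02 | 0.31 | 65.5% | 0.27 | 46.8% |
| 0.05 | 0.25 | 47.7% | 0.15 | 18.1% |
| −0.02 | 0.39 | 84.3% | 0.43 | 84.9% |

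At 3 kg with slope 0, power is 72.6%. With slope 0 there is no bias; the loss is from collinearity alone. With the opposite slope the estimate is inflated and power rises.

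**Results when the true difference from placebo is zero.** The adjusted coefficient then has expectation of size |b| × D. The nominal 5% test rejects in 6.1% (|b| = 0.02) and 11.9% (0.05) of trials at 2 kg, and in 8.6% and 28.5% at 4 kg.

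**Meaning of the 0.5.** The table takes 0.5 as the residual SD of the weight-adjusted model. If it is instead the unadjusted SD, the residual SD is √(0.25 − (b × 3.77)²), and the 4 kg powers become 47.6% and 20.3% at slopes 0.02 and 0.05. If it is the adjusted SD, the unadjusted SD at slope 0.05 is √(0.25 + (0.05 × 3.77)²) = 0.534, and the comparator has 73.2% power, not 78.7%.

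Simulation of the fitted ANCOVA (8,000 runs per scenario) agrees within about 1.5 points.

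**The case against.** The strongest points against are these.

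- **Sample size.** The plan randomises 42 per arm and analyses by intention to treat with last observation carried forward, so up to 42 per arm could be analysed. On the same assumptions power is then 89% without the covariate, 87% (2 kg) or 80% (4 kg) at slope 0, and 58% at 4 kg with slope 0.02. This stands as a qualification of the power figures. It leaves the bias unchanged, and the zero-difference rejection rate at 4 kg and slope 0.05 rises to 36%.
- **Assumed inputs.** The slope has no anchor in the documents. The weight figures come from 8 uncontrolled patients with mean weight 68 kg and mean HbA1c 6.45%, who continued the drug; the one-week pilot change was only 1 kg (P=0.22). This is right: the figures show what is possible, not what to expect.
- **False rejection is conditional.** It needs an effect on weight, a within-arm relation of weight change to HbA1c, and a total HbA1c effect of zero. If the drug changes neither variable, the test keeps its 5% level. This also stands: the fault is a mismatch between model and endpoint, not a general loss of type I error control.
- **The unadjusted t-test is already planned.** So it is, but as a secondary analysis. The plan has no explicit rule for disagreement, and the ANCOVA is the analysis it attaches to the primary endpoint.
- **A weight-independent effect may be of interest.** No aim, hypothesis or endpoint states it, and simple covariate adjustment does not identify it without untestable assumptions.

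**Conclusion.** The concern holds. The primary model conditions on a post-randomisation variable that the protocol itself describes as an effect of the drug, so its coefficient is not in general the contrast that Sections 2.1 and 17.2 describe. This conclusion depends on none of the assumed values. Its numerical consequence does: for 2 to 4 kg, slopes of 0.02 to 0.05 and 32 per arm, the estimate falls to between 0.31 and 0.15 and power to between 66% and 18%. An opposite slope of −0.02 inflates the estimate to 0.39–0.43. Only a zero within-arm slope leaves the estimate unbiased, and power still falls by 3 to 10 points. Because this is the only primary test, it must be corrected.

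**What to change.** In Section 17.1, replace the sentence on weight change with: *The primary ANCOVA of change in HbA1c at 26 weeks will include treatment arm and baseline (screening) HbA1c.* In Section 17.2, state that the residual SD of 0.5 refers to this model. Keep the weight-change-adjusted model, if wanted, only as a labelled exploratory mediation analysis.

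Dropping weight change is the correction. Baseline HbA1c is added for precision and corrects no bias.

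The cost is one replaced sentence, one clarifying sentence and one label. No new data are needed, since HbA1c is already measured at screening and week 26. The amendment should precede the half-way review of endpoint data in Section 19.7. The documents do not give the trial's status; once endpoint data have been seen, the change would be harder to defend as independent of the results.
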